## I. INTRODUCTION

Post-market medical product signal detection – identifying unexpected potential associations between medical product exposures and health outcomes of interest in a real-world population -- is an important component of the U.S. Food and Drug Administration (FDA)'s mission to protect public health. There are multiple post-market signal detection methods that can be implemented in longitudinal healthcare databases to assess potential elevated frequencies of adverse events. These methods can support both cohort and self-controlled designs. Comparisons among methods implemented with stratified cohort designs have been performed, and the methods had similar findings in a small empirical dataset. Three specific signal detection methods that can be utilized with a self-controlled risk interval design, which adjusts for time-invariant confounding, include a) tree-based scan statistics operationalized in TreeScan™, b) Information Component Temporal Pattern Discovery, and c) Sequence Symmetry Analysis. Evaluations have been conducted on each of these methods using longitudinal data, however direct comparisons between these methods have not yet been performed. We propose to conduct an analysis using all three methods with the same empiric and simulated datasets to assess variation in findings.

We chose a clinical study problem to test the methods but emphasize that this project is not intended to be a safety assessment. We will evaluate whether there is an increased frequency of adverse events among new adult users of two oral anti-seizure treatments by comparing a window of time shortly after drug initiation (i.e., the risk window) to referent windows that may occur either prior to or after drug initiation (i.e., the comparison windows).

### II. SPECIFIC AIMS

In a self-controlled risk interval design, only exposed individuals are included, and we will further limit our analysis to newly-exposed individuals. All analyses will treat exposure to the study drug of interest as a point exposure, meaning that any incident drug dispensing, irrespective of the number of days supplied, will be considered a qualifying exposure. Health outcomes of interest will be assessed in a designated risk window as well as several comparison windows occurring before or after the risk window. We will require enrollment during these observation windows to ensure an equal likelihood of observing health outcomes of interest.

#### A. EMPIRICAL COMPARISONS:

We have identified two study exposures of interest and will evaluate these two exposures with all three methods. We will not name a primary analysis as this is a methods evaluation that will involve multiple comparisons varying a) the grouping of outcomes of interest, b) the timing of the referent comparison windows relative to exposure, and c) the length of such windows. A full list of analyses is listed later in this protocol in **Table 1**. The empiric evaluation provides a real-world assessment of the performance of each method when applied to drugs with well-characterized safety profiles.

#### B. SIMULATED DATA ASSESSMENTS:

Using empirical data gathered for the two study exposures of interest, we will choose some outcomes and add investigator-inserted occurrence during the risk window according to a pre-specified simulated association. The occurrence of all other outcomes will be randomized according to their background rate occurrence. The resultant simulated dataset will then consist of "positive" outcomes with pre-specified

associations and the rest will be "null outcomes." We will vary the strength of the simulated association and the prevalence of the outcomes with the simulated association to evaluate the statistical power of the three methods to detect the investigator-inserted elevated frequency. The simulation is important because it evaluates each method's statistical power in detecting known associations that have been artificially inserted at different elevated risk levels.

## III. METHODS

#### A. SURVEILLANCE POPULATION, ENROLLMENT CRITERIA AND STUDY EXPOSURES

Data will be obtained from Optum ClinInformatics from the years 2004 to 2016. We will include individuals who were dispensed the study exposures of interest on or after their 18th birthday during the available date range without further inclusion or exclusion criteria.

There are two study exposures of interest: oral forms of levetiracetam and lamotrigine used in the adult population. Additionally, there is one "calibration" exposure that must be collected to implement one of the methods. The two study exposures were chosen because they have relatively well-characterized safety profiles and are used primarily for treatment for seizure disorders which are medical conditions that are not usually associated with rapid changes in overall clinical status (except for rate of seizures itself). Stability in the expected underlying clinical status is especially important when implementing self-controlled designs to isolate the effect of the exposure itself rather than other temporal confounding factors (e.g., generally declining or improving health state), a concept described in epidemiology as exchangeability. Self-controlled designs compare time periods and it is only a fair comparison when factors outside of the incident dispensing of the study exposure are held as equal as possible through either design or analysis techniques. When the general risk of the health outcomes of interest is equivalent but for the study exposure, then the differences between the observed and expected rate beyond a predefined statistical threshold signifies a potential causal hypothesis requiring further investigation.

Although we will not assess outcomes in the period of time immediately preceding the incident dispensing of the study drug of interest, we still expect that both of these anti-seizure medications may show an increased frequency of seizure-related disorders in the pre-exposure comparison window. Nonetheless, we have chosen to include these outcomes within the groupings of outcomes being assessed. Lamotrigine also has other on- and off-label uses for mood disorders or pain that may create additional time-varying confounding by indication. We expect to triage any increased frequency of these adverse outcomes with these acknowledged limitations.

Only incident exposures of interest will be ascertained, and incidence will be defined as the first oral drug dispensing in 183 days. Patients will be required to be free of any form of the exposure of interest (e.g., intravenous, oral). Exposures of interest will be identified by National Drug Codes (NDCs) and Healthcare Common Procedure Coding System (HCPCS) codes listed in a separate code list document.

Enrollment is required to assess exposure incidence. Enrollment gaps of 45 days or less will be bridged, i.e., treated as continuously enrolled time.

[figure not shown]
Figure 1 is a visual guide to the various parameters that govern how the study cohort is created.

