In general, these outcomes are not considered possibly exposure-associated and so we remove them from the tree to reduce multiple hypothesis testing.

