$$Equation \ 1b \ (Conditional): LLR = \ln\left(\frac{\left(\frac{C_G}{C_G + n_G}\right)^{c_G} \left(\frac{n_G}{C_G + n_G}\right)^{n_G}}{\left(\frac{C}{C + N}\right)^{c_G} \left(\frac{N}{C + N}\right)^{n_G}}\right) I\left(\frac{c_G}{c_G + n_G} > \frac{C}{C + N}\right)$$

Equation 2:  $T = {}^{\max}_{G} LLR(G)$ 

Where: T = Bernoulli tree scan statistic

- G = node of interest
- $c_{\mathsf{G}}$  = number of outcomes in the risk window for a given node  $\mathsf{G}$
- $n_{G}$  = number of outcomes in the comparison window for a given node G
- p = ratio of the risk window length to the entire observation window length
- C = total number of outcomes in the risk window across ALL nodes
- N = total number of outcomes in the comparison window across ALL nodes

*I()* is the indication function, which is 1 when there are more outcomes in the risk window than would be expected by chance. It is included to ensure that we are looking for an excess risk of the having the adverse event rather than a protective decreased risk.

We will use an alerting threshold of p=0.01. In other words, we will evaluate nodes with log-likelihood ratios that fall into the top 1% of the maximal log-likelihood ratios observed using Monte Carlo. These nodes represent the most extreme departures from the null hypothesis.

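### Indication outcomes expected to cluster before exposure stay in the all-node totals of the conditional TreeScan null and can inflate alerts in large unrelated nodes in the 20 pre-exposure-window datasets

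*Protocol*

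**What the plan says.** Section III.A of the protocol states that both drugs "may show an increased frequency of seizure-related disorders in the pre-exposure comparison window". For lamotrigine it adds: "Lamotrigine also has other on- and off-label uses for mood disorders or pain that may create additional time-varying confounding by indication". It then keeps the outcomes in scope, "Nonetheless, we have chosen to include these outcomes within the groupings of outcomes being assessed", and gives the handling: "We expect to triage any increased frequency of these adverse outcomes with these acknowledged limitations".

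Section III.F.1 plans both Bernoulli scan statistics. The unconditional one (Equation 1a) uses the ratio of window lengths as its null. The conditional one (Equation 1b) uses C/(C+N), defined by "C = total number of outcomes in the risk window across ALL nodes" and "N = total number of outcomes in the comparison window across ALL nodes". Both versions are one-sided for an excess in the risk window. Section III.F.2 explains that whole-tree conditioning is there to control for global patterns of healthcare use.

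No section takes indication outcomes out of C and N, and none mentions their effect on other nodes.

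**The concern.** The triage looks at the indication nodes themselves. When their excess lies in the comparison window, the indicator function in Equation 1b sets their statistic to zero, so they do not alert. Their events still enter C and N, however, and so move the reference value for every other node. Any resulting alert appears in a clinically unrelated outcome, where the triage in III.A does not look.

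The incidence rule in III.D can strengthen this: a seizure code before exposure blocks a later code in the same branch within the washout, which removes events from the risk window.

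At stake is the interpretation of the empirical comparison. Section III.G records total alert load and the influence of design choices as results. Section III.E item 1 compares pre- with post-exposure windows, and the two TreeScan versions run side by side. Section III.F.3 sets the SSA cut-off from the larger of the TreeScan and ICTPD alert counts, so extra conditional alerts could also lengthen the SSA list. Without a check, an artefact of indication coding could be read as a property of the method or of the window.

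**Working it through.** The protocol gives no event counts, indication share or alert counts, so there is no figure of its own to reproduce.

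**Inputs from the protocol**
- Risk window: days 1–28 (III.E). Comparison windows: [-56,-29], [-28,-1] or [36,63], each 28 days (Table 1).
- Unconditional null: p = 28/(28+28) = 0.5.
- Alert threshold: 0.01 on the maximum log-likelihood ratio (III.F.1).
- Scope: Table 1 has 15 datasets per study drug, five for each window. Pre-exposure windows: 2 × 10 = 20. Post-exposure: 2 × 5 = 10.

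**Assumptions (not in the protocol)**
- w: share of all counted outcomes in indication branches, 1% to 25%.
- s: fraction of those falling in the risk window, 0.20 to 0.33.
- All other nodes have a true relative rate of 1.

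**Step 1: shifted null.** C/(C+N) = 0.5(1 − w) + w·s. A node with no effect then has an apparent relative rate of (1 − P)/P, where P = C/(C+N).

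| w | s | C/(C+N) | apparent relative rate |
|---|---|---|---|
| 1% | 0.20 | 0.495 + 0.002 = 0.497 | 1.01 |
| 5% | 0.20 | 0.475 + 0.010 = 0.485 | 1.06 |
| 10% | 0.25 | 0.450 + 0.025 = 0.475 | 1.11 |
| 20% | 0.25 | 0.400 + 0.050 = 0.450 | 1.22 |
| 25% | 0.20 | 0.375 + 0.050 = 0.425 | 1.35 |

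**Step 2: single null node.** The critical log-likelihood ratio is approximated by z²/2 at one-sided 0.01/1,000 and 0.01/5,000, giving 9.1 and 10.6. Take 1,000 events and C/(C+N) = 0.45. At 518 risk-window events the statistic is 518·ln(0.518/0.45) + 482·ln(0.482/0.55) ≈ 9.3, which passes 9.1; 517 events do not. For Binomial(1,000, 0.5), P(X ≥ 518) = 13%. For 10.6 the cut-off is 523, with probability 8%. Exact binomial sums give:

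| C/(C+N) | events in null node | alert probability |
|---|---|---|
| 0.500 | 1,000 | about 0.00001 or less |
| 0.485 | 1,000 | 0.01–0.04% |
| 0.475 | 1,000 | 0.13–0.36% |
| 0.450 | 200 | 0.07–0.18% |
| 0.450 | 500 | 0.9–2.2% |
| 0.450 | 1,000 | 8–13% |
| 0.450 | 2,000 | 46–58% |
| 0.425 | 1,000 | 56–68% |
| 0.425 | 2,000 | 98–99% |

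**Step 3: whole tree, by simulation.** The assumed tree has 1,000 unrelated leaves with sizes proportional to 1/rank, 60 parent groups and one indication node. Critical values are the 99th percentile of the maximum from 1,999 null draws. The table shows the chance of at least one false alert in an unrelated node (nominal 0.01), conditional version.

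| w | s | 20,000 outcomes | 100,000 outcomes |
|---|---|---|---|
| 0 | – | 0.006 | 0.017 |
| 5% | 0.33 | 0.010 | 0.013 |
| 10% | 0.33 | 0.027 | 0.44 |
| 10% | 0.20 | 0.24 | 1.00 |
| 20% | 0.33 | 0.41 | 1.00 |

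The unconditional version stayed between 0.003 and 0.020 in these runs. This tree is top-heavy: the sum of 1/rank to 1,000 is about 7.49, so the largest leaf holds about 1/7.49 = 13% of unrelated outcomes. That is why a 10% share already matters here. The first row (w = 0) is what leaving the indication branches out of C and N would give.

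**The case against.** Several objections carry weight.

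- **Conditioning is meant to shift the null.** True, but its stated purpose is global healthcare use. An excess confined to a few indication branches is disease-specific.
- **There are built-in contrasts.** The unconditional run has a fixed null of 0.5 and is immune. Section III.G triages all alerts and records those that hold across comparison windows, and III.H.1 recognises that prior events can change the likelihood of exposure. These are real partial safeguards. However, an alert seen only in the conditional run could reflect either indication spillover or the intended utilisation adjustment, and the contrast cannot separate the two.
- **The size is assumed.** This stands. The tree spans 18 body systems and the incidence rule limits repeat counting, so the share may be low.
- **The pruning in III.C shows no inconsistency.** Codes are dropped there as unlikely to be exposure-associated: "we remove them from the tree to reduce multiple hypothesis testing". That is a different reason; it shows only that pruning is feasible.

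A reader might also infer more than the protocol supports:

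- *That true signals are hidden.* The test is one-sided, so clustering before exposure lowers the null and makes alerts easier. Hiding would need an indication excess in days 1–28 relative to [36,63], which III.A does not predict.
- *That all 30 study-drug datasets are affected.* The stated seizure expectation concerns the pre-exposure window, hence 20.
- *That the power results are distorted.* Power is assessed in simulated data, where the other outcomes are randomised at background rates (II.B). On a plain reading the imbalance is not carried over.
- *That pruned runs should replace the planned ones.* Whole-tree conditioning is the method under evaluation, and replacing it would evaluate something else.

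**Conclusion.** The point holds for conditional TreeScan in the 20 study-drug datasets with a pre-exposure window. With all-node totals, the seizure excess that the protocol itself expects must lower C/(C+N), other things equal, and no section deals with the effect on unrelated nodes. Whether this matters in practice depends on w, s and node size, none of which is given. In the cases checked it is negligible at indication shares of 1–5%, small at about 10% except in very large nodes or datasets, and large at 20–25%. These figures assume that all other nodes are truly null; the single-node probabilities also use an approximate critical value, and the whole-tree results use an invented tree. The point warrants a pre-specified sensitivity check, not a change to the planned analyses.

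**What to change.** 1. Keep every planned run as it is, and keep those runs as the basis for conclusions.
2. Before data extraction, fix a list of indication branches: seizure/epilepsy for both drugs, plus mood-disorder and pain branches for lamotrigine.
3. For the 20 study-drug datasets with a pre-exposure window, add a conditional sensitivity run that leaves these branches out of the tree, and so out of C and N.
4. Report C/(C+N) with and without the branches for each of these datasets.
5. Flag unrelated-node alerts that disappear in the pruned run as possible indication spillover when interpreting the conditional-versus-unconditional and pre-versus-post comparisons.

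The cost is one fixed list and 20 extra runs on data already collected. The indication nodes are not tested by the conditional statistic in the added runs, but they stay in the planned conditional and unconditional runs. If the indication share proves small, the two sets of results should agree closely and show it.

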#### B. RISK AND COMPARISON WINDOWS

We are interested in examining multiple risk and comparison windows within the study period. A complete list of analyses is shown in **Table 1** below and illustrated in **Figure 1**. All windows are defined relative to the study exposure index date (i.e., Day 0). Inclusion of time in these windows includes whole weeks such that weekend or weekday days are equally represented.

#### Figure 1. Design Diagram

#### C. STUDY OUTCOMES IN A HIERARCHICAL DIAGNOSIS TREE

Use of a tree structure with hierarchical groupings of clinically related potential adverse events is inherent to TreeScan. The tree structure does two things: 1) it declares an outcome to be incident with respect to itself as well as clinically related groupings and 2) it eliminates the need for an investigator to prespecify how a clinician might record similar outcomes in the billing record (i.e., claims data) across thousands of different outcomes. Use of such trees is compatible with all three methods under consideration; we therefore will define outcomes based on their clinical grouping in the Multi-Level Clinical Classification System (MLCCS).

[figure not shown]
Outcomes will be identified using ICD-9-CM codes and ICD-10-CM codes. All ICD-9-CM diagnoses are classified into a hierarchical tree structure defined by the MLCCS. The MLCCS is a product of the Agency for Healthcare Research and Quality's Healthcare Cost and Utilization Project (http://www.hcup-us.ahrq.gov/toolssoftware/ccs/ccs.jsp). It is a hierarchical system with four aggregate diagnosis levels, although on some branches there may only be two or three levels. The first and broadest level identifies 18 body systems, while the entries at the finest level contain one or multiple ICD-9-CM codes. For

- 3 -

Sentinel Methods Protocol

example, as can be seen in **Figure 2**, five different ICD-9-CM codes make-up the aggregate concept of "convulsions" which has the same grouping of outcomes at both the 3rd and 4th level of the MLCCS tree.

To use the MLCCS tree, we mapped ICD-10-CM codes to ICD-9-CM codes, using the Centers for Medicare & Medicaid Services' General Equivalence Mappings (GEMs). The mapping scheme was finalized prior to extracting the data and conducting the analyses.

Some ICD-9-CM and ICD-10-CM codes were excluded from the tree and therefore from the analysis, for example, those representing:

- Some conditions unlikely to manifest themselves within the short follow-up time we are dealing with, such as cancer.
- History of pre-existing conditions (e.g., codes with nomenclature that refers to previously diagnoses medication conditions usually given as "History of...").
- Other outcomes very unlikely to be caused by exposure, such as well-care visits and normal delivery of an infant.

In general, these outcomes are not considered possibly exposure-associated and so we remove them from the tree to reduce multiple hypothesis testing.

#### D. INCIDENT OUTCOMES OF INTEREST

This study will focus on incident outcomes that occur in either the risk or comparison windows, i.e., collectively the observation window. An incident outcome is defined as one that was observed in the pre-defined settings (see **Table 1**) during the observation window with no other outcomes in the same level and branch of the MLCCS tree in any setting during a pre-set number of prior days. We will perform analyses using both the fourth and fifth level, separately, as the incident outcome assessment level. The fourth level signifies that a never-before-seen ICD-9-CM code is not counted if a unique ICD-9-CM code

[figure not shown]

belonging to the same level was observed during the outcome washout window. This prevents double counting of very closely related outcomes such as if someone were coded as having experienced both ICD-9-CM 780.3 (i.e., convulsions) and ICD-9-CM 780.31 (i.e., febrile convulsions) within a few days' time. **Figure 2** shows their relationship with each other with respect to the tree. Both of these codes are in the same 4th level node so only the first incident code within this grouping will be included in the analytic data set. Each member can contribute multiple incident outcomes in the risk and comparison windows as long as these outcomes are not part of the same branch of the MLCCS tree (**Figure 3**).

#### **Figure 3. Counting Incidence Outcomes**

Hypothetical example where incidence is defined at level 2

- Patient has 4 ICD9 diagnosis claims (leaf level) occurring in the exposure risk window
- At leaf level, patient contributes 2 outcomes, 1) the first occurring ICD9 code for A1, A2, A3 and 2) B4
- Patient contributes 2 outcomes at level 2, A and B

In rare situations where multiple incident outcomes on the same level of the tree in the same branch are experienced *on the same day,* then only one outcome is allowed to enter the analysis and a tie-breaker procedure is needed. The outcome is selected according to a priority list, which is based on outcome frequency. Tie-breaker procedures are expected to be invoked infrequently. As a rule of thumb, the rarest incident outcome is defined as the priority outcome because nodes with rare outcomes are more impacted by incremental increases in count levels.

Additionally, we will perform an analysis at the fifth level, which treats each code as incident with respect to itself only and not a clinically related grouping of outcomes. However, this fifth level will still invoke mapping from ICD-10-CM to ICD-9-CM otherwise nearly every ICD-10-CM diagnosis would automatically be counted as an incident diagnosis.

More outcomes will be observed when the analysis is performed at the fifth level since the incidence criteria are less stringent.

Outcomes will not be counted that occur during the outcome blackout window. This window provides separation between the risk window and the post-exposure comparison window and is used frequently in epidemiologic studies designed to study particular exposure-outcome pairs when the window lengths can be tailored for particular outcomes of interest. In a signal detection framework evaluating thousands of outcomes with different onset times, this window is admittedly arbitrary but retained for consistency with familiar designs.

Two outcome washout windows will be used to define incident outcomes: 183 days and 400 days. Enrollment will be required for the entire duration of the outcome washout. The 183-day washout has the advantage of garnering a larger sample size because less continuous enrollment is required. The disadvantage is that many chronic health conditions that are coded infrequently in a person's medical

history will be misclassified as incident outcomes because they will not have been coded within 183 days. The 400-day washout window was selected to minimize capture of chronic health conditions by looking for less frequent medical encounters that represent follow-up visits chronic disease management. A longer washout window that captures these annual visits will have the trade-off of reducing the sample size because of continuous enrollment requirements.

